4.14. Retinopathy

A retinal exam will be performed by an ophthalmologist as part of the screening procedures (performed up to 6 months prior to Day 0) to exclude proliferative retinopathy, severe non-proliferative retinopathy from any cause (ETDRS retinopathy score > 35), clinically significant macular edema or previous pan retinal photocoagulation therapy. The ETDRS retinopathy score will be recorded. The exam will be repeated 0-14 days before the Month 12 and Month 18 visits. Subjects are not to receive study product at the Month 12 visit until the report has been reviewed.

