5.10. Dosing Visit Study Procedures: Month 12 (\pm 7 days)

ALL PROCEDURES FOR THE MONTH 12 VISIT ARE THE SAME AS THOSE OF THE MONTH 3 VISIT (See Section 5.6).

In addition to the procedures in Section 5.6, the following procedures should also be performed pre-dose:

- Retinopathy Exam

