5.14. Follow-Up Visit Study Procedures: Month 18 (\pm 7 days)

1. Medical History
2. Physical Examination
3. Peripheral Vascular Intervention Update
4. Assessment of CLI (associated measurements are listed separately)
5. Ulcer/gangrene and Index Leg Photography (after debridement, if necessary)
6. Retinopathy Examination
7. Hemodynamic Measurements
8. QOL Measurements (VascuQol Questionnaire)

9. Ischemic Rest Pain severity measured using the VAS pain scale (see Appendix E)
10. Collect Laboratory Test samples for the following: Hematology, Chemistry, CBC, Urinalysis, and an anti-HGF antibody
11. Adverse Event review
12. Concomitant Medication review
13. Weight and Vital Signs assessment

5.15. Assessments to Complete Prior to a Planned Intervention (Surgical Revascularization or Major Amputation)

1. Details of planned Intervention (type, date, etc)
2. Assessment of CLI (associated measurements are listed separately)
3. Ulcer/gangrene Photographs of Index Leg (after debridement)
4. Angiogram Assessment
5. Hemodynamic Measurements
6. QOL assessment using VascuQol Questionnaire
7. Ischemic Rest Pain severity measured using the VAS pain scale
8. Adverse Event review
9. Concomitant Medication review
10. Weight and Vital Signs assessment

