6. SCREEN FAILURES AND SUBJECT WITHDRAWALS

6.1. Withdrawals

A subject may refuse any or all treatment or study procedures at any time during the study. Participation is voluntary, and refusal to participate will involve no penalty or loss of benefits to which the subject is otherwise entitled. *A subject who refuses to participate after receiving one or more doses of the study product should be encouraged to continue follow-up as per protocol including the safety follow-up program (See Section 10) Safety Follow-up Program regarding safety follow-up procedures).*

If the subject wishes to withdraw study consent, every effort must be made to encourage the subject to return to the study site for safety evaluation purposes for all remaining study visits. Subjects who wish to withdraw from the study prematurely and have had at least one dose of study product will be requested to return to the study site for study specific safety and efficacy assessments.

If the subject withdraws prior to Month 6, the procedures for the Month 6 visit should be completed as the exit visit. If the subject withdraws between Month 6 and Month 18, the procedures for the Month 18 visit should be completed as the exit visit. Additionally, every effort will be made to obtain and record information regarding revascularization by surgery, major

amputation, myocardial infarction, stroke, and death even if the subject does not return for an exit visit. In case any of these events have occurred, evidence from source documents will be obtained for confirmation. Prior informed consent will have been obtained from the subject to gain access to these documents. If the subject refuses any continued study participation, decline of study participation should be documented in writing. If the subject refuses to communicate with the study site, final attempts to contact the subject should be documented with a certified letter to the subject's last known address.

The Principal Investigator is permitted to discontinue the subject from receiving study product for medical reasons at any time. However, the subject will continue to return for protocol dictated follow-up visits for the remainder of the total study period (18 month visit) including the safety follow-up program.

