2.4.3 Study Day, Analysis Visit Windows and Baseline

Subject visits will be analyzed by nominal visit and/or time point as recorded on the CRFs, given that the day on which the visit occurs falls into the appropriate window as described in the table below. If a visit date does not fall into the correct window, data from that visit will not be summarized in the tables, but it will be included in the listings.

Study Day will be calculated from the reference date, and will be used to show the start and stop day of assessments and events.

The reference date is defined as the day that the first injection is administered, that is, Day 0.

Study Day = (date of event – date of Day 0).

The analysis will utilize less stringent visit windows than defined in the protocol, as defined below. If a subject has more than one visit in a visit window, the visit closest to the scheduled day will be considered for the analyses. If the difference is a tie, the day before the scheduled day will be used in the statistical analyses.

Unless otherwise specified, baseline is defined as the last non-missing measurement taken prior to reference start date (excluding unscheduled assessments). In the case where the last non-missing measurement and the reference start date coincide, that measurement will be considered pre-baseline, but Adverse Events (AEs) and medications commencing on the reference start date will be considered post-baseline.

Unscheduled visit measurements will not be used to provide a measurement for either baseline values or post-treatment values. Unscheduled data will be included in the standard subject listings but not in the summary tables.

Table 2 Visit Window

Analysis Visit	Scheduled Day	Start of Window (Study day)	End of Window (Study day)
Screening	-30	-30	<0
Day 0	0	0	0
Month 3	90	80	100
Month 6	182	167	197
Month 9	273	258	288
Month 12	365	335	395
Month 15	455	420	490
Month 18	548	503	593
LTFU 1 (Month 24)	730	685	775
LTFU 2 (Month 30)	912	867	957
LTFU 3 (Month 36)	1095	1050	1140

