2.5.5 Efficacy Analysis

- Ulcer improvement**

A table showing the number of subjects completely healed in the target ulcer will be provided at up to 6 months, > 6 months to 12 months, from >12 months to 18 months. If available, the number of subjects with at least 20% reduction in bi-dimensional size (by measuring largest diameters) will be provided. The reduction in bi-dimensional size will be calculated by taking the product of the largest diameters for each baseline and postbaseline measurement, then subtracting the baseline result from the postbaseline result.

- Ischemic Rest pain (of the index leg) using a 10 cm VAS scale**

Rest pain severity will be assessed at the specified predetermined time points. Rest pain severity will also be assessed prior to surgical revascularization or major amputation (of the index leg). A table showing the number of subjects reduced by ≥ 20 mm from baseline in VAS score will be provided at up to 6 months, > 6 months to 12 months, from >12 months to 18 months. Summary statistics will be provided for baseline and change from baseline for each visit and LOCF. One sample t-test for change-from-baseline will be performed. If death occurs, the worst score prior to death instead of last observation will be carried forward.

- Hemodynamic Measurements**

Summary statistics will be provided for baseline and change from baseline for hemodynamic parameters (right/left brachial systolic pressure, ankle systolic pressure measured at dorsalis pedis and posterior tibial, toe systolic pressure, calculated ABI, and calculated TBI) by visit. At each visit, only subjects who have a non-missing value at both baseline and the specific visit will be summarized. Two-sided one-sample t-test will be performed for each visit and LOCF.

- Subjects with any worsening CLI event of index leg**

A summary table and listing of worsening CLI-related events of the index leg including any new or worsening events, worsening rest pain, new ulcer or worsening ulcer, new or worsening wound infection, peripheral vascular intervention, complication of a peripheral vascular intervention, cellulitis, and amputation due to worsening CLI will be provided.

- Subjects who either died, had MI, Stroke, revascularization (by surgical bypass, by endovascular intervention, by hybrid procedure), major amputation, or all-cause death**

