- Blood chemistry: glucose (fasting), uric acid, total cholesterol, HDL, calculated LDL, triglycerides, aspartate transaminase (AST), alanine aminotransferase (ALT), calcium, phosphorus, total bilirubin, alkaline phosphatase, total protein, albumin, globulin, lactic acid dehydrogenase (LDH), serum creatinine, creatinine clearance (estimated using the Cockcroft-Gault formula), blood urea nitrogen (BUN), and electrolytes (Na^+ , K^+ , Cl^-).

- **Physical Examination**

The number of subjects with abnormalities will be provided for the following visit windows: Day 0 to Day 42, Month 3 to Month 3+42 Days, Month 6, Month 9 to Month 9+42 Days, Month 12 to Month 12+42 Days, Month 15, and Month 18/ET. A listing of subjects with abnormalities will be presented.

- **Retinopathy Examination**

Summary statistics will be provided for baseline and change from baseline for Early Treatment Diabetic Retinopathy Study (ETDRS) score by visit. At each visit, only subjects who have a non-missing value at both baseline and the specific visit will be summarized. The number and percent of normal, abnormal (clinically significant, not clinically significant, and all) retinopathy examinations will be presented for baseline, Month 12, and Month 18. A listing of ETDRS scores and abnormalities will also be provided.

AnGes

AMG0001 Protocol AG-CLI-0209
STATISTICAL ANALYSIS PLAN, FINAL Ver. 1

Statistical Analysis Plan Signature Page

This Statistical Analysis Plan has been prepared in accordance with team reviewers' specifications.

Document Authors		
[name] Project Statistician PharPoint Research, Inc.	SIGNATURE:  DocuSigned by:  [name] Signer Name: [name] Signing Reason: I approve this document Signing Time: 22-Mar-2018 11:37 AM EDT 4AB99FDC32904E00AB3D4FED13A6402C	Date (ddmmmyyyy) 22-Mar-2018 11:37 AM EDT
[name] AnGes USA Statistics AnGes USA Inc.	SIGNATURE: 	Date (ddmmmyyyy) 2 April, 2018
Review/Approvals		
[name] Reviewing Statistician PharPoint Research, Inc.	SIGNATURE: 	Date (ddmmmyyyy) 22 Mar 2018
[name], MS Director of Clinical Operations AnGes USA Inc.	SIGNATURE: 	Date (ddmmmyyyy) 22 March 2018
[name] [name], MPH Managing Director AnGes USA Inc.	SIGNATURE: 	Date (ddmmmyyyy) 22 March 2018

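### SAP retinopathy tables have no early-termination row: a retinal exam at an exit visit between Month 6 and about Day 502 is listed but not tabulated, unless it is mapped to Month 12

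*SAP*

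**What the plan says.** - **Exit visit.** Protocol 6.1: "If the subject withdraws between Month 6 and Month 18, the procedures for the Month 18 visit should be completed as the exit visit". The Month 18 list in Protocol 5.14 contains "6. Retinopathy Examination". For a withdrawal before Month 6 the exit visit follows the Month 6 list (Protocol 5.7), which has no retinal exam.
- **Retinopathy tables.** SAP 2.5.7 plans counts and percentages of normal and abnormal results, split by clinical significance: "retinopathy examinations will be presented for baseline, Month 12, and Month 18". It also plans ETDRS score and change by visit without naming the visits, using only subjects with values at both baseline and that visit. Scores and abnormalities are listed as well.
- **Windows.** SAP 2.4.3: "If a visit date does not fall into the correct window, data from that visit will not be summarized in the tables". Such data, and unscheduled data, go to the listings only. Table 2 sets Month 12 at Days 335–395 and Month 18 at Days 503–593, and has no early-termination visit.
- **Month 12 exam.** It comes before that visit's dose. Protocol 4.14: "Subjects are not to receive study product at the Month 12 visit until the report has been reviewed". Protocol 5.10 places it among the items for which "the following procedures should also be performed pre-dose".
- **Contrast.** The physical examination summary in SAP 2.5.7 ends with "Month 12 to Month 12+42 Days, Month 15, and Month 18/ET", so an early-termination category exists there.

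**The concern.** Safety is a primary objective, and Protocol 8.1 notes that the angiogenic potential of the product is unknown. The retinal exam is a direct check for such an effect. The protocol treats it that way: it excludes ETDRS scores above 35, holds the Month 12 dose until the retinal report has been read, and asks about eyesight in long-term follow-up.

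Only two retinal exams are scheduled after dosing starts, at Month 12 and Month 18. For a subject who leaves in between, or before Month 12, the exit exam is the last one and may be the only one after dosing. The SAP rules remove that exam from the summary because the subject left early. A clinically significant finding at such an exam would not be in the clinically significant count, and the subject would also drop out of the Month 18 denominator.

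**Working it through.** **1. The plan's windows reproduce.** Protocol 9.2.3 and SAP Table 2 agree: 365 − 30 = 335 and 365 + 30 = 395; 548 − 45 = 503 and 548 + 45 = 593.

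**2. Possible exit days.** Both documents define a month as 30 days, so Month 6 = Day 180 and Month 18 = Day 540. That gives 540 − 180 + 1 = 361 days.

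**3. Injection sets by exit day.** Target dosing days are 0, 14, 28, 42, 90, 104, 118, 132, 270, 284, 298, 312, 360, 374, 388 and 402: 16 sets × 4 mg = 64 mg.

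| Exit day | Days | Share of 361 days | Sets received | Exit exam in the tables? |
|---|---|---|---|---|
| 180–334 | 155 | 42.9% | 8–12 | No |
| 335–395 | 61 | 16.9% | 12–15 | Only if mapped to Month 12 |
| 396–502 | 107 | 29.6% | 15–16 | No; at most the Month 12 exam |
| 503–540 | 38 | 10.5% | 16 | Yes, Month 18 |

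Check: 155 + 61 + 107 + 38 = 361. These are shares of calendar days, not of subjects.

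**4. Days 180–502 alone.** 155 + 61 + 107 = 323 days.
- If an exit visit on Days 335–395 may count as Month 12, 155 + 107 = 262 days (262/323 = 81.1%) lead to no tabulated exit exam.
- If the exit visit carries the Month 18 label and must fall in the Month 18 window, all 323 do.

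Mapping to Month 12 is only a partial rescue. When two visits share a window, SAP 2.4.3 takes the one closer to the scheduled day (365), and the earlier one in a tie. With the Month 12 visit on Day 360 (5 days away), an exit visit on Days 370–395 is 5 to 30 days away and loses to the pre-dose exam.

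**5. Exposure not covered by a tabulated exam.**
- Exit on Days 180–334: 8–12 sets, that is 32–48 of 64 mg, with no tabulated exam after any of them.
- Exit on Days 396–502: the Month 12 exam follows 12 sets. 15 − 12 = 3 to 16 − 12 = 4 sets (12–16 mg; 12/64 = 18.8% to 16/64 = 25%) have no tabulated exam after them.

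**6. Weight of one subject.** 1/10 = 10% to 1/8 = 12.5%. Illustration, assuming one affected subject with a clinically significant exit finding and everyone else tabulated as normal: the Month 18 row shows 0 of 7–9, while a row that included exit exams would show 1 of 8–10.

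**7. How firm each table's omission is.** For the normal/abnormal table it is explicit, because the time points are named. For the ETDRS change summary it is inferred from Table 2 and the out-of-window rule.

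**The case against.** The strongest reply is that nothing is lost. In a single-centre, open-label, descriptive pilot of 8–10 subjects, a listing is close to a full readout, and this SAP presents laboratory safety data by listing alone. Retinal worsening that meets the adverse event definition would enter the treatment-emergent tables. SAP 2.5.7 also promises a table and line listing of subjects who discontinued, and SAP 2.5.2 tabulates numbers in the study over time, so a short denominator would be visible. All of this stands and limits the consequence. It does not remove the gap: the SAP chose to tabulate retinopathy, the adverse event tables do not give ETDRS change or exam counts, and the discontinuation summary is not said to carry retinal results.

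Four stronger readings are tempting and are not supported:

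- *A mandatory exam is discarded.* Protocol 6.1 words the exit procedures as something that should be done, and subjects may refuse any procedure. The result is also kept in the listing.
- *Most leavers are affected.* The 81% counts calendar days. The documents give no withdrawal rate.
- *The SAP withholds from retinopathy a last-observation analysis that it gives elsewhere.* For hemodynamics it does say "Two-sided one-sample t-test will be performed for each visit and LOCF", and the retinopathy paragraph has nothing similar. But Protocol 9.2.2 plans carry-forward for continuous data under a heading that covers efficacy and safety. Whether that reaches ETDRS is unresolved, and nothing shows that carry-forward would admit an out-of-window exit value.
- *The tables would report no worsening.* That needs an affected subject with a finding, which is only the illustration in step 6.

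**Conclusion.** The point holds as a gap in the safety tables, not as a loss of data. Under SAP 2.4.3 and 2.5.7 as written, an exit retinal exam on Days 180–334 or 396–502 is listed but not tabulated, and one on Days 335–395 is tabulated only if mapped to Month 12. Leavers in the first range then have no post-dose retinal result in the tables. Leavers in the range 396–502 have at most the pre-dose Month 12 exam.

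This rests on 30-day months, on-target dosing, and windowing by visit date as SAP 2.4.3 states. If the exam date were windowed instead, the bounds would shift slightly, because Protocol 4.14 lets the scheduled exams precede the visit by up to 14 days.

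Not affected: subjects taken off study product who keep attending, on-schedule exams, and exits from Day 503. Withdrawals before Month 6 have no exit retinal exam, so no SAP change helps them. No endpoint, test or data collection is in question. This is a cheap improvement worth making because the summary serves a primary safety objective and each subject is 10–12.5% of the cohort.

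**What to change.** Leave the baseline, Month 12 and Month 18 rows and the listing as they are, and add to SAP 2.5.7:

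> Retinal exams at an exit visit are summarised regardless of the Table 2 windows in a separate row, last post-dose exam (ET included), for ETDRS change and normal/abnormal counts; study day and number of injection sets received are listed.

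The cost is one sentence and one table row, using exams that the protocol already calls for. The documents do not say whether the database has been locked. If it has, the row can be added as a labelled supplementary summary.

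The downside is that the row mixes follow-up of about 6 to 18 months and 8 to 16 injection sets. That is why it should stand apart from the Month 18 row. Relabelling that row Month 18/ET, as for physical examination, is not a good substitute: without an explicit override the Table 2 window would still exclude the exit exams, and with one the mixing would enter the Month 18 row itself.
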